7.2. Secondary Objective

- 1) To perform a cost-effective analysis of MCC v EGD.
- 2) To measure patient satisfaction for EGD v MCC.
- 3) To measure 30-day safety.
- 4) To compare international trials that compared EGD to MCC for detection of gastric lesions.
- 5) To measure the time required to visualize the stomach for MCC versus EGD.

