8. STUDY OUTCOME MEASURES

8.1. Primary Outcome:

Aim 1: Pilot and Feasibility Stage.

- 1) *Implementation:* Installation, Training, Site Requirements
- 2) *Practicality:* Duration of MCC test (minutes), Technician “learning curve,” Clinical Staff and Patient Satisfaction, Duration of fasting required
- 3) *Integration:* Scheduling MCC, Linkage with EGD follow-up, Image storage, Image transfer, Documentation of Interpretation, Photo-documentation, Database development

Aim 2: High-Quality Visualization (90%) of Gastric Anatomic Landmarks

Defined as visualization and photo-documentation of the following anatomical landmarks:

- 1) Lower Esophagus / Z line
- 2) Cardia / fundus
- 3) Body, lesser curvature AND/OR Body, greater curvature
- 4) Anterior / Posterior walls
- 5) Angularis
- 6) Antrum
- 7) Pylorus
- 8) Duodenal Bulb
- 9) Duodenal Ampulla

Aim 3: MCC versus EGD for visualization of anatomic landmarks (see above) and gastric lesions in symptomatic patients

Defined as visualization and photo-documentation of the following structures and diseases:

- 1) Visible Lesions (Paris Classification if relevant)
- 2) Ulcers (Forrest Classification) erosions
- 3) Gastric Atrophy
- 4) Gastric Varices
- 5) Gastritis*
- 7) Submucosal lesions
- 8) “Does patient need a follow-up EGD?” Y/N (Opinion of endoscopist interpreting MCC based on MCC findings.)

* (not erythema but ‘chicken wire’ pattern intramucosal change in vascular pattern or hemorrhagic)

8.2. Secondary Outcomes:

- (1) Cost-effective analysis

- (2) 30-day follow-up for adverse events and safety
- (3) Patient Satisfaction of MCC versus EGD
- (4) Replication of similar sensitivity and specificity of MCC to EGD to prior trials outside of the US for (a) Ulcers; (b) Cancer; (c) Inflammatory Changes
- (5) Time spent visualizing the stomach for MCC versus EGD (minutes)
- (6) Visualization of the duodenum
- (7) Hiatus hernia

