8.3. Selected Outcomes Measures (see data collection sheets)

8.3.1. Procedure time.

- When measuring procedure time of EGD and MCC, we will consider all components of procedure including anesthesia, prep, cleaning and preparing room for next patient and turn-around time. We will also measure total time for staff and for the clinician.

8.3.2. Training to perform MCC.

- How long? How many cases needed? Is there a learning curve to speed and accuracy?

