8.3.3. Fasting and MCC prep

- NPO Midnight the day before MCC.

8.3.4. Scoring Anatomic Regions.

After confirming that gastric emptying has been achieved with overnight fast -- we will use the 5-point visualization score described in Ching, 2019 for the following anatomic regions

- Lower Esophagus / Z line
- Corpus
 - Greater curvature
 - Lesser Curvature
- Anterior Wall
- Posterior Wall
- Proximal stomach
 - Cardia/Fundus
- Distal Stomach
 - Antrum/Pylorus/Angularis
- Duodenum
 - Bulb
 - Ampulla

8.3.5. Scoring Gastric Mucosal lesions.

("yes/no")

- Visible Lesions (Paris Classification if relevant)
- Ulcers (+/- Forrest Classification)
- Gastric Atrophy
- Gastric Varices
- Gastritis*
- Hiatus hernia
- Submucosal lesions
- Plus: Does patient need endoscopic intervention?

8.3.6. Lesions picked up by MCC and not by EGD.

- Healing lesions (especially ulcers) are natural course of disease therefore we assume that some

lesions will be detected by capsule but not by EGD if EGD is done a few days later. With photo-documentation and two independent readers, we hope to assure that this phenomenon is a natural course of lesion and not a "false-positive" by MCC.

8.3.7. Measuring patient satisfaction (see *MAGNET7 and 8, day 7 and 30*).

- I felt the research team answered all my questions. Yes No
- Did you feel any pain with swallowing? Yes No
- How difficult was it to swallow the capsule? Very Easy Moderately Easy Neutral Moderately Difficult Very Difficult
- Did you feel discomfort after swallowing while operator moved the capsule? Yes No
- Did you notice the capsule pass during a bowel movement?? Yes No
- Any other issues? Yes No
- If yes, what were the issues? _____
- How much time in total approximately did you have to take out during your day for the capsule endoscopy procedure? _____ (we do not ask this)
- Did you feel like you needed to miss work after the capsule endoscopy procedure? Yes No (we do not ask this)
- Did you need someone to take you home after the capsule endoscopy procedure? Yes No (we do not ask this) In the future, if both studies were equally accurate and you needed another examination of your stomach, would you prefer to have a traditional EGD or a capsule? EGD Capsule. Why?

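### The protocol sets out to compare patient satisfaction between EGD and MCC, but none of the satisfaction items listed as asked rates the EGD experience

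*Protocol*

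**What the plan says.** Protocol section 7.2 gives as secondary objective 2: "To measure patient satisfaction for EGD v MCC". Section 8.2 repeats it as secondary outcome 3: "Patient Satisfaction of MCC versus EGD". Separately, section 8.1 includes "Clinical Staff and Patient Satisfaction" among the Aim 1 practicality outcomes, with no comparison attached.

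Section 8.3 is headed "Selected Outcomes Measures (see data collection sheets", so it presents itself as a selection and points to forms that are not reproduced. Within it, section 8.3.7 says how patient satisfaction is measured. It assigns the items to forms Magnet 7 and Magnet 8, the Day 7 and Day 30 calls. A typical item is "Did you feel discomfort after swallowing while operator moved the capsule". Three items carry a note that they are not asked. The last item asks the patient to suppose that the two tests are equally accurate and then to choose: "would you prefer to have a traditional EGD or a capsule? EGD Capsule. Why".

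Section 9.4, step 6, also has satisfaction assessed when the MCC is completed. The steps on EGD (8 and 9) cover performing the procedure and storing its images.

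**The concern.** The objective has two arms, and the listed instrument measures one of them. A comparison of satisfaction with EGD and with MCC needs some report from the patient about each. The list has several about the capsule and none about the EGD. The only place where the two procedures meet is a single forced choice about a future examination.

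A preference shows which test patients would pick under an assumed condition. It does not show how satisfied they were with either one. If every patient were content with both and slightly favored the capsule, the answers could look the same as if every patient had found the EGD unpleasant.

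If the forms match the list, secondary objective 2 cannot be answered as written. No choice of analysis can repair this, because the EGD responses would not exist. Section 20 also lists patient satisfaction as a planned publication topic, so the comparison has an intended use.

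**Working it through.** No sample size, power or error-rate figure bears on this point. The check is an item count of section 8.3.7 against the objective, followed by a search of the rest of the protocol for an EGD satisfaction measure.

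**Item count.** The follow-up on what the other issues were is counted separately, and the preference question with its request for a reason is counted as one item.

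| Item in 8.3.7 | Concerns | Asked? |
|---|---|---|
| Research team answered questions | General | Yes |
| Pain with swallowing | Capsule, by context | Yes |
| Difficulty swallowing the capsule (five levels) | Capsule | Yes |
| Discomfort while the capsule was moved | Capsule | Yes |
| Noticed the capsule pass | Capsule | Yes |
| Any other issues | General | Yes |
| What the issues were | General | Yes |
| Total time taken from the day | Capsule | Marked not asked |
| Needed to miss work | Capsule | Marked not asked |
| Needed someone to take them home | Capsule | Marked not asked |
| Future choice between EGD and capsule | Preference | Yes |

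- Listed: 4 capsule + 3 general + 3 not asked + 1 preference = 11.
- Asked: 11 − 3 = 8, made up of 4 + 3 + 1.
- Items rating the EGD experience: 0 of 8 asked, and 0 of all 11 listed. The three unasked items are worded for the capsule procedure only, so restoring them as they stand would not help.
- Items in which EGD is named: 1, the preference question.

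**Search elsewhere.**

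- Section 8.3.1 does treat the two procedures in parallel: "When measuring procedure time of EGD and MCC, we will consider all components of procedure". It then adds "We will also measure total time for staff and for the clinician". These are procedure components and staff time, not patient reports.
- Section 9.4, step 6, places a satisfaction assessment at the end of the MCC, and no matching step follows the EGD.
- In Appendix B, the title of the EGD form (Magnet 6) refers to EGD and lesion assessment, not to satisfaction.

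**Timing of the preference item.** Section 9.4 allows up to 14 days between the two procedures, in either order. A Day 7 answer can therefore come before an EGD done later in that window, whereas a Day 30 answer comes after any EGD within it. Section 8.3.7 does not say which call supplies the comparative answer. Section 13.2 expects some drop-out before EGD, so some respondents may answer without having had the study EGD.

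**The case against.** The strongest reply is that the forms are not shown. Section 8.3 calls its measures selected, 8.3.7 refers to Magnet 7 and 8, and three entries are marked as not asked, so the list is plainly not a copy of the forms. This stands, and it limits the point to the listed items. A reader might infer that the trial collects no EGD satisfaction data at all; the document does not establish that.

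The second reply is that preference is a legitimate within-patient comparison. The objective fixes no scale and does not ask for paired ratings, and section 6.3.1 reports a preference figure (95.7% favoring the capsule) from a prior multicenter study. This also stands in part: the preference item is worth keeping. But the objective names satisfaction, and a choice under assumed equal accuracy does not measure satisfaction with either procedure.

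The third reply concerns weight. This is one of several secondary outcomes in a 72-patient proof-of-concept study with no formal inference planned (section 13.2). That limits the consequence, but the gap lies in what is measured rather than in precision, so the pilot status does not close it.

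Three further inferences would go too far. EGD is not absent from the list, since the preference item names it. MCC is not left unrated, since it has a five-level swallowing scale and yes/no items. And timing does not invalidate the preference data, since the Day 30 call follows every EGD within the window.

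**Conclusion.** The point holds for the items as listed. Of 8 items asked, 0 rate the EGD experience and 1 compares the procedures, hypothetically. These data would support a description of MCC tolerability and the proportion preferring each test. They would not support a comparison of satisfaction with each procedure, which is what secondary objective 2 and secondary outcome 3 state. The capsule items remain suitable for the non-comparative satisfaction outcome under Aim 1. Visualization, lesion comparison and safety are unaffected.

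The conclusion rests on two assumptions: that Magnet 7 and 8 match the list apart from the items marked as not asked, and that the swallowing-pain item refers to the capsule. If the forms already contain EGD ratings, correcting section 8.3.7 would settle the matter. If the swallowing-pain item is classed as general, the split changes but the count of EGD ratings stays at zero.

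**What to change.** On an existing follow-up call made after both procedures, ask a short set of items that apply to both, at least overall satisfaction and discomfort, once for MCC and once for EGD. Take the comparative preference answer from that same call, and flag participants who had no EGD so that their answers are reported separately. Keep the items on swallowing, capsule movement and passage as MCC tolerability.

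If EGD items are not added, restate secondary objective 2 and secondary outcome 3 as MCC tolerability plus stated preference. This is a change of wording only.

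Adding the items costs a slightly longer call and a form revision for IRB review; no new visit or procedure is needed. Two limits would remain. Recall intervals for the two procedures would differ by the gap between them, up to 14 days within the allowed window. And because EGD may be done under sedation (section 6.3.3), the discomfort comparison would need cautious reading.

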9. STUDY DESIGN

9.1. Study Design

Prospective Study of Diagnostic Utility of MCC

9.2. Proposed Site

George Washington University (GWU) Medical Faculty Associates (MFA) in Washington, DC.

9.3. Patient Safety

The study will be conducted in compliance with the Declaration of Helsinki, ICH-GCP guidelines, ISO 14155, and US regulations. Study design will be approved by the local IRB at each participating institution prior to commencement.

9.4. Study procedure:

1. Screen potential adult patients with an appropriate indication for upper endoscopy such as epigastric pain/burning, nausea and or vomiting, bloating, heartburn, iron deficiency anemia, unintended weight loss, abnormal imaging suggesting organic disease from a larger pool of patients seen in an ED, Urgent Care, Primary Care and GI Clinic patients. In some settings, a research assistant will be on site to perform the screen. In other settings, the clinical staff will perform the screen or potential patients will be contacted by phone by RC. (Form used: *Magnet 1*)
2. Patients screened who are eligible will be approached about potential interest. (See *full list of inclusion/ exclusion criteria*). In some circumstances, patients will be given contact information for the research coordinator (RC), who will contact them as soon as possible to schedule MCC. In other circumstances, the research assistant will contact RC and attempt to schedule MCC before patient leaves the clinical setting.
3. RC will contact patients to complete screening, confirm eligibility, obtain verbal consent, and schedule both MCC and EGD (if EGD is not already scheduled). Formal written consent will be obtained by patient at the MCC location ([name]).
4. Participants arrive at the MCC location for final screen, sign written consent and undergo MCC. All consented patients will be given a study ID and recorded in enrollment log. (Form used: *Magnet 3*) The patient's demographics and images will be stored in a HIPAA compliant fashion.
 - BRIEF DESCRIPTION OF MCC PROCEDURE. The patient will be NPO midnight. They will come to the facility and will ingest the capsule per manufacturer's protocol. (Manufacturer's protocol says that the person will take 10ml of simethicone in 100ml of water 40min before capsule is ingested. The capsule will then be controlled externally by magnetic field by the examining health care provider in such a way that the major regions of the stomach are photo-documented with still images and video. This may involve changing the position of the patient and the

possible ingestion of additional water. The sequence of the examination

will be pre-determined, and each area will have a predetermined number of images obtained as suggested by Gastroenterology Society guidelines.

5. Patient data collected will include the following elements: chief complaint of patient, history of present illness, past medical history, current medications (only PPIs and pain medication)..
6. At completion of MCC, video will be archived and patient satisfaction will be assessed. Capsule endoscopy will NOT be used for clinical decisions.
7. Patients will be instructed to return to the physician sooner, if concerning signs develop. A 7 and 30-day follow-up call and chart review is only performed if person is lost to follow-up will be conducted to check for symptom resolution and adverse events.
8. Esophagogastroduodenoscopy (EGD) will be performed as soon as possible in an appropriate endoscopy facility by an experienced endoscopist.
9. Endoscopic images will be stored in secure serve for later comparison with MCC images.

Summary of Research Strategy

- ❖ PRE-SCREEN (DAY -7 to DAY -1)
 - Upper Abdominal Pain or Related Symptoms (Indications for an EGD)
 - Performed in ED, UC, PCP offices or GI clinic
- ❖ SCREEN (DAY -7 -> DAY 0)
 - More thorough screening questions and scheduling by RC (<24 hours)
 - Performed by Telephone
- ❖ ENROLL (DAY 0)
 - Signed Informed Consent procedure, more detailed questions and MCC Procedure performed
 - Occurs at the GWU Medical Faculty Associates Building on [name].
 - NaviCam MCC performed by trained Clinician.
 - Reviewed by a Gastroenterologist.
 - Scheduled for an EGD will ideally be performed within 5 days of the MCC procedure, but will allow MCC procedure to be performed up to 14 days either before or after an EGD (paid by insurance as standard of care).
- ❖ FOLLOW-UP (DAY 1-30)

- Day 7 and Day 30: Telephone Call plus CRISP Chart Review, only if lost to follow-up.

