22.2. APPENDIX B – Document List (per request)

Magnet 1: Magnet potential patient form

Magnet 2: Patient eligibility screening

Magnet 3: Patient Data Collection Form

Magnet 4: Anatomic and Lesion Assessment (A)

Magnet 5: Anatomic and Lesion Assessment (B)

Magnet 6: EGD and Lesion Assessment (C)

Magnet 7: Patient Follow-up Call Day 7

Magnet 8: Patient Follow-up Call Day 30

Magnet 9: Patient CRISP Chart Review

Magnet 10: Adverse Event Form/ Serious Event Form

Magnet 11: Protocol Deviation

Magnet 12: Lost to Follow-up

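### The Aim 3 landmark comparison is at risk of favouring MCC, because photographs are part of the success definition but only MCC has an image-acquisition rule

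*Protocol*

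**What the plan says.** **Endpoint (Protocol 8.1).** Aim 2 landmark success is "Defined as visualization and photo-documentation of the following anatomical landmarks", followed by nine landmarks. Aim 3, also listed as a primary outcome, is "MCC versus EGD for visualization of anatomic landmarks (see above) and gastric lesions in symptomatic patients". Its own definition line, which introduces the lesion list, again asks for both elements: "Defined as visualization and photo-documentation of the following structures and diseases".

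**Scoring (8.3.4).** Anatomic regions are to be graded on a published 5-point visualization score. The section does not say whether EGD is scored in the same way, or from which images.

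**MCC imaging (9.4).** The capsule is steered so that "the major regions of the stomach are photo-documented with still images and video". The examination sequence is set in advance, and "each area will have a predetermined number of images obtained as suggested by Gastroenterology Society guidelines". In addition, "At completion of MCC, video will be archived and patient satisfaction will be assessed".

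**EGD imaging (9.4).** An experienced endoscopist performs the EGD. The only statement about its images is "Endoscopic images will be stored in secure serve for later comparison with MCC images". Section 6.3.1 describes the EGD as standard of care, billed to the insurer.

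**Timing (9.4).** MCC may take place up to 14 days before or after EGD. Written consent is signed at the MCC visit.

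**The concern.** Whether a landmark counts under 8.1 depends on two things: whether it was seen, and whether an image of it was kept. For MCC, the second is governed by a study procedure. For EGD, it is left to routine practice. A difference between the tests on this endpoint can therefore reflect how routinely endoscopists photograph normal anatomy, and not what EGD can see. MCC could look equal or better on a primary aim while being worse.

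The consequences are descriptive but real. Section 13.2 says that Aim 3 pilots the non-inferiority concept for a larger study, and section 20 lists a planned pilot non-inferiority paper on anatomic landmarks. A photograph that was never taken cannot be recovered at analysis. Image acquisition and form content must be settled before data are collected, so this belongs in the protocol and cannot be left to a statistical analysis plan.

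**Working it through.** The protocol states no landmark rate for EGD, no photograph rate, no margin and no power, so there is no figure of its own to reproduce. The check has two parts.

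**1. The text, item by item**

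| Element | MCC | EGD |
|---|---|---|
| Photograph in the endpoint definition | Yes (8.1) | Yes, if Aim 3 carries over the whole Aim 2 definition (8.1) |
| Sequence fixed in advance | Yes (9.4) | Not stated |
| Number of images per area | Yes (9.4) | Not stated |
| Video archived | Yes (9.4) | Not stated |
| Images stored | Yes (9.4) | Yes (9.4) |
| Can precede written consent | No | Yes, by up to 14 days (9.4) |

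EGD has a storage rule but no acquisition rule. The MCC rule is stated for regions of the stomach. Three of the nine landmarks (lower esophagus/Z line, duodenal bulb, duodenal ampulla) lie outside it, so the asymmetry is clear for the other six.

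**2. Illustration of size**

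For one landmark, counted rate = P(seen) × P(photographed, given seen).

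All inputs are assumptions: EGD sees the landmark in 98% of patients, MCC sees it in 90%, and MCC photographs everything it sees. The true EGD-minus-MCC difference is then 98 - 90 = +8 points.

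| EGD photograph rate | EGD counted rate | Apparent EGD minus MCC (points) |
|---|---|---|
| 100% | 0.98 × 1.00 = 98.0% | +8.0 |
| 95% | 0.98 × 0.95 = 93.1% | +3.1 |
| 90% | 0.98 × 0.90 = 88.2% | -1.8 |
| 80% | 0.98 × 0.80 = 78.4% | -11.6 |
| 70% | 0.98 × 0.70 = 68.6% | -21.4 |

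The ranking reverses when 0.98 × p < 0.90, that is p < 0.90/0.98 = 91.8%.

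As a second case, assume that both tests truly see the landmark in 95% of patients. The artefact in favour of MCC is then 0.95 × (1 - p). It is 0 points at p = 100%, 9.5 at 90%, 19 at 80% and 28.5 at 70%. If all 72 participants had both tests, the last three would be about 7, 14 and 21 patients (72 × 0.095 = 6.8; 72 × 0.19 = 13.7; 72 × 0.285 = 20.5).

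Scoring both tests on visualization alone removes the factor p, and the artefact in this model becomes zero. Any real difference in visualization remains.

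**The case against.** The strongest reply has five parts.

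- **The rule is not explicit for EGD.** Nowhere does the protocol say that a landmark seen but not photographed at EGD is scored as not seen. The Aim 3 heading speaks of visualizing landmarks and points back to Aim 2. That pointer could import the list alone or the full definition, and the Aim 3 definition line introduces lesions. This stands: the bias is conditional on the stricter reading. The text does not exclude that reading, so the ambiguity itself needs settling.
- **Section 8.3.4 uses a graded score.** A 5-point visualization score is not a photographed yes/no. This also stands, and the fix should use that score. It does not remove the problem, because the section does not say how, or from what material, EGD is scored.
- **The EGD form may already list landmarks.** A reader might infer from Appendix B that it does not, because the title of Magnet 6 mentions lesions but not anatomy. The form is not shown, and a title does not settle its content, so no weight is put on it.
- **Routine EGD may photograph nearly everything.** If so, the artefact is small. At a 95% photograph rate EGD still leads by about 3 points in the first illustration, so reversal is possible but not shown.
- **Aim 3 is a pilot.** Section 13.2 plans no formal inference. This limits the harm to descriptive results and later planning. It does not repair the comparison.

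**Conclusion.** The point holds as a risk. The endpoint includes a photograph, MCC has a rule to secure one, and EGD has none. If the photograph requirement is applied to EGD, any error from landmarks seen but not photographed at EGD runs in favour of MCC. A reader might infer that the comparison is definitely biased, or that MCC will come out ahead. The documents support neither, because they give no EGD photograph rate and do not say outright that unphotographed EGD landmarks fail.

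Under the assumptions of 98% and 90% true visualization and complete MCC photography, the apparent EGD-minus-MCC difference runs from +8 points at a 100% EGD photograph rate to about -21 at 70%, and changes sign near 92%. The asymmetry is firmest for the landmarks within the stomach. It should be corrected, because the remedy is cheap and missing images cannot be supplied later.

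**What to change.** 1. **In 8.1, 8.3.4 and 9.4**, make visualization the Aim 3 landmark comparison for both tests, with the same landmark list and the same 5-point score. Report photo-documentation as a separate result for each test.
2. **For EGDs done after written consent**, have the endoscopist record the landmark list on the EGD form (Magnet 6, if it is not already there), and request the same landmark images as for MCC.
3. **For EGDs done before written consent**, where no study form or image request could apply, score from the procedure report and stored images, flag these patients, and show the comparison with and without them.

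The cost is a form revision and a little endoscopist time per EGD. No extra procedure or reader is needed.
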